5.5 SAMPLES FOR GENETIC/GENOMIC ANALYSIS

5.5.1 Description of the scope of genetic/genomic analysis

The research correlates for this study are expected to include DNA/RNA sequencing of tumors, including circulating tumor (ct) DNA. In addition, whole exome sequencing may include evaluation for known lymphoma mutations. For any genetic studies performed, the results will be deposited in a database such as dbGaP per NIH requirements. Although there is controlled access to such a database, such a submission carries theoretical risks of revealing the identity of the subject. This is discussed in the consent.

5.5.2 Description of how privacy and confidentiality of medical information/biological specimens will be maximized

Confidentiality for genetic samples will be maintained as described (Section 5.4.2). In addition, a Certificate of Confidentiality has been obtained for this study.

5.5.3 Management of Results

Subjects will be contacted if a clinically actionable gene variant is discovered. Clinically actionable findings for this study are defined as disorders appearing in the American College of Medical Genetics and Genomics recommendations for the return of incidental findings that is current at the time of primary analysis. (A list of current guidelines is maintained on the CCR intranet: <https://ccrod.cancer.gov/confluence/display/CCRCRO/Incidental+Findings+Lists>).

5.5.4 Genetic Counseling

Subjects will be contacted with a request to provide a blood sample to be sent to a CLIA certified laboratory. If the research findings are verified in the CLIA certified lab, the subject will be offered the opportunity to come to NIH to have genetic education and counseling to explain this result; at the time of any such event(s), these activities will be funded by the NCI/CCR in consideration of the specific circumstances. If the subject does not want to come to NIH, a referral to a local genetic healthcare provider will be provided (at their expense).

This is the only time during the course of the study that incidental findings will be returned. No interrogations regarding clinically actionable findings will be made after the primary analysis.

6 DATA COLLECTION AND EVALUATION

6.1 DATA COLLECTION

6.1.1 Summary

The PI will be responsible for overseeing entry of data into an in-house password protected electronic system (C3D) and ensuring data accuracy, consistency and timeliness. The principal investigator, associate investigators/research nurses and/or a contracted data manager will assist with the data management efforts. Primary and final analyzed data will have identifiers so that research data can be attributed to an individual human subject participant.

All adverse events (AEs), including clinically significant abnormal findings on laboratory evaluations, regardless of severity, will be followed until return to baseline or stabilization of event.

Document AEs from the first study intervention through 30 days after the last study intervention was administered. Beyond 30 days after the last intervention, only adverse events which are serious and related to the study intervention need to be recorded.

End of study procedures: Data will be stored according to HHS, FDA regulations, and NIH Intramural Records Retention Schedule as applicable.

Loss or destruction of data: Should we become aware that a major breach in our plan to protect subject confidentiality and trial data has occurred, this will be reported expeditiously per requirements in section [7.2](#).

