3.5.1 Safety Follow-Up Visit

The safety follow-up visit should occur 30 days (\pm 7 days) after the last dose of trial treatment, or before the initiation of a new anti-cancer treatment, whichever comes first. Required testing is as noted in the Study Calendars (Section [3.6](#)). All AEs that occur prior to the Safety Follow-Up Visit should be recorded. Patients with an ongoing, treatment-related AE of Grade $>$ 1 will be followed until the resolution of the AE to Grade 0-1, stabilization of the AE in the opinion of the investigator, or until the beginning of a new anti-neoplastic therapy, whichever occurs first. SAEs that occur within 30 days of the end of treatment or before initiation of a new anti-cancer treatment should also be followed and recorded.

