3.5.2 Extended Safety Follow-up

Given the potential risk for delayed immune-related toxicities, safety follow-up must be performed up to 90 (+14) days after the last dose of avelumab administration. This may be performed either via a clinic visit or via a telephone call with subsequent clinic visit requested in case any concerns are noted during the telephone call.

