8.2 ASSESSMENT OF SAFETY EVENTS

AE information collected will include event description, date of onset, assessment of severity and relationship to study product and alternate etiology (if not related to study product), date of resolution of the event, seriousness and outcome. The assessment of severity and relationship to the study product will be done only by those with the training and authority to make a diagnosis and listed on the Form FDA 1572 as the site principal investigator or sub-investigator. AEs occurring during the collection and reporting period will be documented appropriately regardless of relationship. AEs will be followed through resolution.

SAEs will be:

- Assessed for severity and relationship to study product and alternate etiology (if not related to study product) by a licensed study physician listed on the Form FDA 1572 as the site principal investigator or sub-investigator.
- Recorded on the appropriate SAE report form, the medical record and captured in the clinical database.
- Followed through resolution by a licensed study physician listed on the Form FDA 1572 as the site principal investigator or sub-investigator.

For timeframe of recording adverse events, please refer to section [6.1](#). All serious adverse events recorded from the time of first investigational product administration must be reported to the sponsor with the exception of any listed in section [8.4](#).

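### A 90-day contact is required to look for delayed immune-related toxicity, but non-serious immune-related events starting more than 30 days after the last intervention need not be recorded and can be missing from the primary AE frequencies

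*Combined protocol and SAP*

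**What the plan says.** Section 3.5.2 gives the reason for extended follow-up, "Given the potential risk for delayed immune-related toxicities", and makes it compulsory: "safety follow-up must be performed up to 90 (+14) days after the last dose of avelumab administration". The contact can be light: "This may be performed either via a clinic visit or via a telephone call". Footnote 1 of the Study Calendar (Section 3.6) repeats the 90-day contact.

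Section 6.1.1 sets the recording rule in two parts. Full recording is limited in time: "Document AEs from the first study intervention through 30 days after the last study intervention was administered". After that, "only adverse events which are serious and related to the study intervention need to be recorded".

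Section 3.5.1 has much the same scope: "All AEs that occur prior to the Safety Follow-Up Visit should be recorded", with that visit due at day 30 (±7). Section 8.2 adds no window of its own: "For timeframe of recording adverse events, please refer to section" 6.1.

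The primary objective (Section 1.1.1) covers the toxicity profile as well as the MTD. Section 10.1 lists the number and percentage of treatment-emergent AEs as a primary endpoint, and Section 10.4.2 tabulates them by severity and relationship. Sections 10.1, 10.3.1 and 10.4.2 do not say when the treatment-emergent window ends.

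**The concern.** The follow-up schedule and the recording rule do not fit together. The protocol asks staff to look for delayed immune-related events over roughly three months, but requires full recording for only the first of them. An event that is related and clinically managed, but not serious, need not be recorded if it starts after day 30.

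By the protocol's own standards such events matter. Table 13 withholds avelumab and starts systemic steroids for a Grade 2 immune-related event, Table 12 starts hormone treatment for Grade 1 or 2 endocrinopathies, and Section 14.2.2 names immune-mediated reactions as important risks of avelumab.

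What is at stake is the toxicity-profile half of the primary objective. An unrecorded event cannot enter the Section 10.4.2 tables, so an omission can only lower the count. Because recording such events is optional, capture may also vary between patients and staff, which makes the resulting percentage hard to interpret.

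**Working it through.** The point rests on reading the sections together. The plan gives no figure for late immune-related events, so there is none to reproduce. The arithmetic shows the length of the gap and, under assumed rates, how easily it could matter at this sample size.

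**1. Does another section close the gap?**
- Section 3.5.1 follows ongoing related events above Grade 1. That covers events already present at the day-30 visit, not those that start later.
- Section 8.2 refers back to Section 6.1.
- Section 8.1.2 keeps an event if it is serious, including important medical events by judgment. Section 8.5.1 has Hy's Law cases reported as SAEs.
- No section exempts immune-related events from the rule or requires non-serious findings at the 90-day contact to be recorded.

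The gap therefore remains for non-serious events with onset after day 30.

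**2. Length of the gap**, when avelumab is the last intervention:
- To day 90: 90 − 30 = 60 days.
- To the end of the contact window: (90 + 14) − 30 = 74 days.

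For six cycles on schedule, the last avelumab dose falls on study day 5 × 28 + 22 = 162. Full recording ends on day 162 + 30 = 192, and the contact falls between days 162 + 90 = 252 and 162 + 104 = 266.

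The two windows also have different anchors: recording runs from the last study intervention, the contact from the last avelumab dose. If rhIL-15 was given last, the gap is somewhat shorter.

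**3. Illustration.** Inputs are 9 patients at the MTD and an accrual ceiling of 30 (both Section 10.2), and an assumed probability p that a patient has a non-serious immune-related event in the gap that goes unrecorded.

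Chance of at least one such patient among 9 = 1 − (1 − p)^9; expected number among 30 = 30p.

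| Assumed p | At least one of 9 | Expected among 30 |
|---|---|---|
| 5% | 1 − 0.95^9 = 0.37 | 1.5 |
| 10% | 1 − 0.90^9 = 0.61 | 3.0 |
| 15% | 1 − 0.85^9 = 0.77 | 4.5 |

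This treats patients as independent, all followed to the contact, with every such event left unrecorded. If staff record half of them anyway, an event rate of 10% acts like p = 5%, and 61% falls to 37%.

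**4. What does not change.** DLTs count only in the first 28 days (Section 3.1.1), so the escalation rule, the MTD and the sample size are untouched.

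**The case against.** The strongest reply is that the two sections serve different purposes. The 90-day contact is patient surveillance, by telephone if need be, with a clinic visit if something is found. The data rule keeps what is serious and related. Several parts of that reply stand:

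- A reader might infer that delayed immune-related events as a class drop out of the toxicity profile. The documents do not support that. Serious related events are kept at any time, lack of hospitalisation does not make an event non-serious, and everything with onset through day 30 is recorded.
- The rule permits omission; it does not forbid recording.
- Some late laboratory abnormalities may surface elsewhere. As far as the extracted calendar can be read, chemistry and thyroid tests continue in follow-up before progression, and the Section 10.4.2 shift tables have no day-30 cut-off. That does not help with rash or colitis, or with patients who have progressed.
- A reader might also infer that the plan discards most of what the contact would show, or that a reported immune-related event rate is biased by a known amount. Neither is supported. The documents do not split late events by seriousness and define no immune-related frequency endpoint, and the treatment-emergent window is left open at its end.

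The reply does not remove the mismatch. The important-medical-event route is discretionary and will not reliably capture outpatient Grade 2 events. If the treatment-emergent window was meant to close at day 30, the plan should say so. As written, it is unclear whether even a recorded serious late event enters the primary table.

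**Conclusion.** The mismatch between Sections 3.5.2 and 6.1.1 is real and no other section resolves it. Non-serious immune-related events with onset more than 30 days after the last intervention need not be recorded. They can be absent, unevenly between patients, from the primary AE frequencies, and any omission works downward.

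The scope is limited: a period of 60 to 74 days when avelumab is given last, non-serious events only, and no effect on dose escalation or the MTD. The size of the shortfall cannot be estimated from the documents. The 37%, 61% and 77% are chances of at least one omission among 9 patients at assumed rates of 5%, 10% and 15%, not estimates of bias. The conclusion that events can be lost rests on the text alone; the conclusion that the primary table understates them also assumes that the table is meant to cover this period.

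**What to change.** Three linked changes, all to data capture and reporting:

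1. Amend Section 6.1.1 so that all immune-related AEs regardless of seriousness, and related AEs of Grade 3 or higher, are recorded through the 90 (+14)-day contact, counted from the last avelumab dose. After that contact, only serious related AEs need be recorded. Align Section 3.5.2 with this.
2. State in Sections 10.1 and 10.4.2 when the treatment-emergent window ends.
3. In Section 10.4.2, tabulate events with onset more than 30 days after the last intervention separately, so that the fully recorded period and the selectively recorded period are not pooled unmarked.

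The cost is protocol wording and a few extra CRF entries at a contact that already takes place. No visit, sample size, escalation rule or treatment rule changes. Recording after day 30 would still be selective, which is why the separate table is needed.

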6.1.2 Data Collection/Recording Exceptions

6.1.2.1 Abnormal Laboratory Values

An abnormal laboratory value will be considered an AE **only** if the laboratory abnormality is characterized by any of the following:

- Results in discontinuation from the study
- Is associated with clinical signs or symptoms
- Requires treatment or any other therapeutic intervention
- Is associated with death or another serious adverse event, including hospitalization
- Is judged by the Investigator to be of significant clinical impact

- If any abnormal laboratory result is considered clinically significant, the investigator will provide details about the action taken with respect to the test drug and about the patient's outcome.

6.2 DATA SHARING PLANS

6.2.1 Human Data Sharing Plan

What data will be shared?

I will share human data generated in this research for future research as follows:

Coded, linked data in an NIH-funded or approved public repository.

Coded, linked data in another public repository

Coded, linked data in BTRIS (automatic for activities in the Clinical Center)

Identified or coded, linked data with approved outside collaborators under appropriate agreements.

How and where will the data be shared?

Data will be shared through:

An NIH-funded or approved public repository. Insert name or names: [ClinicalTrials.gov](#), [dbGaP](#).

BTRIS (automatic for activities in the Clinical Center)

Approved outside collaborators under appropriate individual agreements.

Publication and/or public presentations.

When will the data be shared?

Before publication.

At the time of publication or shortly thereafter.

6.2.2 Genomic Data Sharing Plan

Unlinked genomic data will be deposited in public genomic databases such as dbGaP in compliance with the NIH Genomic Data Sharing Policy.

6.3 RESPONSE CRITERIA

6.3.1 Response Assessments

Tumor response will be assessed by the investigator using the RECIL 2017 criteria (52) for all patients with T-cell lymphoma other than CTCL. Global Response Score (53), and modified severity weighted assessment tool (mSWAT) (11) will be used for patients with CTCL. Patient will be re-evaluated for response as outlined in the Study Calendar, Section [3.6](#).

6.3.2 Response Criteria for PTCL and ALCL

RECIL 2017 criteria (52) use the Deauville five-point scale for assessment of response via FDG-PET. The five-point scale (5-PS) has been validated for use at interim staging and at the end of treatment and was adopted as the preferred reporting method at the First International Workshop on PET in Lymphoma in Deauville, France (i.e., Deauville criteria), and in several international trials.

The 5-PS PS scores the most intense uptake in a site of initial disease:

1. if present, as follows: no uptake or no residual uptake (when used at interim)
2. slight uptake, but below blood pool (mediastinum)
3. uptake above mediastinal, but below or equal to uptake in the liver
4. uptake slightly to moderately higher than liver
5. markedly increased uptake or any new lesion (on response evaluation)

The sum of longest diameter (SLD) is used for assessment of tumor burden. In patients with disseminated disease, a maximum of three target lesions should be selected and used to estimate tumor response. Target lesions should be selected from those with the largest size that can be reproducibly measured and preferably representing multiple sites and/organs. In most cases, lymph nodes can be considered target lesions if the lymph node longest diameter measures ≥ 15 mm. A lymph node measuring between 10 and 14 mm is considered abnormal but should not be selected as a target lesion. Lymph nodes measuring <10 mm in diameter are considered normal. In certain anatomical sites (inguinal, axillary, and portocaval), normal lymph nodes may exist in a narrow, elongated form, and such nodes should not be selected as target lesions if alternatives are available. Extranodal lesions are selected as target lesions if they have soft tissue component, based on their size, and the ease of reproducibility of repeated measurements, with a minimum measurement of the longest diameter of ≥ 15 mm. All other lesions should be identified as nontarget lesions and should be recorded at baseline, without the need to measure them. Nontarget lesions should be followed and reported as present, absent, or clear progression.

Table 14: Response categories based on assessment of target lesions

% Change in sum of diameters of target lesions from nadir					
	CR	PR	MR	SD	PD
% change from baseline	
 • Complete disappearance of all target lesions and all nodes with long axis <10 mm • $\geq 30\%$ decrease in the sum of longest diameters of target lesions (PR) with normalization of FDG-PET 	$\geq 30\%$ decrease in the sum of longest diameters of target lesions but not a CR	$\geq 10\%$ decrease in the sum of longest diameters of target lesions but not a PR ($<30\%$)	$<10\%$ decrease or $\leq 20\%$ increase in the sum of longest diameters of target lesions	
 • $>20\%$ increase in the sum of longest diameters of target lesions • For small lymph nodes measuring <15 mm post therapy, a minimum absolute increase of 5 mm and the long diameter should exceed 15 mm • Appearance of a new lesion
FDG-PET	Normalization of FDG-PET (Deauville score 1-3)	Positive (Deauville score 4-5)	Any	Any	Any
Bone marrow involvement	Not involved	Any	Any	Any	Any
New lesions	No	No	No	No	Yes or No
CR, complete response; CT, computerized tomography; FDG-PET, [18F]2-fluoro-2-deoxy-D-glucose; MR, minor response; PD, progression of disease; PR, partial response; SD, stable disease.					

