⁹ Physical exams to include medical history (i.e., complete at Screening/Baseline; interim on study and in follow-up), vitals, weight, and height (screening only). ECOG to be recorded at least once per cycle, on day 1, 8, and/or 22.

¹⁰ Chemistry panels include: Acute care, Hepatic, and Mineral.

¹¹ Diffusing capacity/alveolar volume (DLCO/VA), forced expiratory volume in 1 second (FEV1) for patients with significant pulmonary or smoking history.

¹² At screening a CT scans of neck, chest, abdomen, and pelvis should be performed (with IV and PO contrast, unless patient is allergic or has renal insufficiency; other imaging may be substituted at the discretion of the investigator). Other body areas may be imaged if clinically indicated. MRI of the brain is only required in patients with suspected involvement of CNS. Also, at screening, a FDG-PET/CT torso (extremities to be included if there is confirmed or suspected disease involvement). At baseline one or more of the following studies: CT, MRI, FDG-PET/CT and or clinical photography.

¹³ Patients with neurological symptoms or signs should undergo MRI scan of the brain and lumbar puncture.

¹⁴ Baseline bone marrow aspiration/ biopsy with flow cytometry must be done within 3 months prior to starting treatment. During post-treatment follow-up, repeat bone marrow aspiration/ biopsy needed only to confirm a CR.

¹⁵ Peripheral blood flow cytometry may be done for disease evaluation of patients who had circulating leukemic cells detected at baseline, and for patients with CTCL regardless of their baseline results.

¹⁶ To be performed in selected patients with cutaneous disease (as determined by PI or AI).

¹⁷ Dermatology assessment and Global/mSWAT scoring will be used instead of or in addition to radiologic evaluation for patients with predominantly cutaneous disease

¹⁸ Samples for correlative research are to be collected as indicated in Section 5. Prior biopsy specimen blocks will be used for PD-L1 staining if available. If archival tissue is not available or adequate, baseline punch biopsy of the skin or core needle biopsy of a lymph node/visceral lesion is required, otherwise this is optional.

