6.3.5 Best Overall Response

The best overall response is the best response recorded from the start of the treatment until disease progression/recurrence (taking as reference for progressive disease the smallest measurements recorded since the treatment started). The patient's best response assignment will depend on the achievement of both measurement and confirmation criteria.

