12.5.2 Risks from Radiation Exposure

The procedures for performing the chest CT and ¹⁸F-FDG PET/CT scans will follow clinical policies, no special procedures apply to these additional assessments for research purposes. In summary, subjects may receive additional radiation exposure from up to six (6) additional CT scans of the neck, chest, abdomen, and pelvis, and three (3) additional ¹⁸F-FDG PET/CT scans.

The total additional radiation dose for research purposes will be approximately 11.4 rem.

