PD	$>50\%$ increase in size (SPD) of any organs involved at baseline OR New organ involvement OR Loss of response: $>50\%$ increase from nadir in the size (SPD) of any previous organ involvement in those with PR (whichever occurs first)
Relapse	New organ involvement in those with CR

Abbreviations: CR, complete response; PR, partial response; SPD, sum of the maximum linear dimension (major axis) \times longest perpendicular dimension (minor axis); SD, stable disease; PD, progressive disease.

Response in Blood*	
Response	Definition
CR†	B_0
PR‡	≥50% decrease in quantitative measurements of blood tumor burden from baseline in those with high tumor burden at baseline (B_2)
SD	Fails to attain the criteria for CR, PR, and PD
PD§	B_0 to B_2 or > 50% increase from baseline and at least 5,000 neoplastic cells/ μ L or Loss of response: in those with PR who were originally B_2 at baseline, > 50% increase from nadir and at least 5,000 neoplastic cells/ μ L
Relapse	Increase of neoplastic blood lymphocytes to $\geq B_1$ in those with CR

Abbreviations: CR, complete response; PR, partial response; SD, stable disease; PD, progressive disease.

* As determined by absolute number of neoplastic cells/ μ L

† If a bone marrow biopsy was performed at baseline and determined to unequivocally be indicative of lymphomatous involvement, then to confirm a global CR where blood assessment now meets criteria for B_0 , a repeat bone marrow biopsy must show no residual disease or the response should be considered a PR only.

‡ There is no PR in those with B_1 disease at baseline as the difference within the range of neoplastic cells that define B_1 is not considered significant and should not affect determination of global objective response.

§ Whichever occurs first

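### Table 14 makes a positive PET a condition of PR, so a non-CTCL patient with at least 30% shrinkage, a negative PET and involved marrow fits no response category

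*Combined protocol and SAP*

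**What the plan says.** Section 6.3.1 has the investigator score every patient other than those with CTCL by RECIL 2017, and Table 14 in section 6.3.2 is the protocol's statement of those categories. Its cells, for a patient with no new lesion, are:

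- **CR:** target lesions gone, or at least a 30% decrease with a normalised PET. The PET row reads "Normalization of FDG-PET (Deauville score 1-3", and the marrow must be uninvolved.
- **PR:** in the size row, at least a 30% "decrease in the sum of longest diameters of target lesions but not a CR". The PET row reads "Positive (Deauville score 4-5". Marrow may be in any state.
- **MR:** at least a 10% "decrease in the sum of longest diameters of target lesions but not a PR", with the cap of 30% spelled out. PET and marrow may be in any state.
- **SD:** less than a 10% decrease, up to a 20% increase. PET and marrow may be in any state.

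Footnote 14 of the Study Calendar (section 3.6) says that in post-treatment follow-up a "repeat bone marrow aspiration/ biopsy needed only to confirm a CR". For CTCL, the footnote to the blood table in Appendix C covers a marrow that was involved at baseline: "a repeat bone marrow biopsy must show no residual disease or the response should be considered a PR only". Section 6.3.2 has no matching sentence.

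ORR, defined as CR plus PR, is the first secondary endpoint in section 10.1. ORR in tumours with at least 50% PD-L1 expression and duration of response build on it.

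**The concern.** The PR column gives two different rules. The size row makes PR whatever is left when CR is not met. The PET row makes PR available only when PET is positive. They agree as long as PET alone separates CR from PR, but CR has a second condition, the marrow. A patient who fails CR on marrow alone has a negative PET, so the PET row also shuts that patient out of PR.

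The result is perverse. Of two patients with the same shrinkage and the same involved marrow, the one with the worse PET is a responder and the one with the better PET has no category. If the table is applied as written, true responders are lost from the ORR numerator. If it is not, the classification rests on unwritten investigator judgement in an open-label trial.

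**Working it through.** The plan states no target response rate or power for ORR, so there is no figure to reproduce. The check is whether Table 14 classifies every patient.

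**Step 1: apply the table.** All rows of a column are required together, with no new lesion. For a decrease of at least 30% (including complete disappearance of target lesions):

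| PET | Marrow clear | Marrow involved | Marrow unknown |
|---|---|---|---|
| Deauville 1-3 | CR | none | none |
| Deauville 4-5 | PR | PR | PR |
| Not done | none | none | none |

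Every combination with a 10% to <30% decrease is MR, and every stable combination is SD, whatever the PET or marrow. The gap affects only patients with a decrease of at least 30%.

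**Step 2: can these patients arise?**

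- *Negative PET, marrow involved.* Footnote 14 says follow-up marrow is repeated to confirm a CR, so it is done in patients who already look like complete responders. A positive result there puts the patient in the empty cell.
- *PET not done.* PET/CT is listed at screening (section 2.2.4). At baseline it is one of several options (section 2.4.3). No section requires it at the 8-weekly evaluations or at the confirmatory scan 4 weeks after a first response (Study Calendar, footnote 4). This gap is per visit: section 6.3.5 takes the best response from start of treatment to progression, so a visit with PET can still supply a CR or PR.

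**Step 3: effect on ORR.** Section 10.4.3 requires a section of the report on all eligible patients, so an unclassified patient stays in the denominator and leaves the numerator. The cost per patient is 1/N:

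- N = 27 (maximum evaluable, section 10.2): 1/27 = 3.7 points
- N = 9 (planned size of the MTD group): 1/9 = 11.1 points

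With the plan's 95% Agresti-Coull interval and an assumed one-third of patients responding, all scored by Table 14:

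- 9/27 = 33.3% (18.5 to 52.3); one lost, 8/27 = 29.6% (15.7 to 48.7); two lost, 7/27 = 25.9% (12.9 to 44.9)
- 3/9 = 33.3% (11.7 to 64.9); one lost, 2/9 = 22.2% (5.3 to 55.7)

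**Step 4: how many patients?** The documents give neither the rate of marrow involvement nor the rate of PET-marrow discordance. For scale only, assume an ORR of 25% to 33% (the range spanned by romidepsin in section 1.2.2 and the phase II nivolumab trial in PTCL in section 1.2.5), marrow involvement in 10% to 30%, and a negative PET with marrow still involved in 25% to 50% of those. Expected loss = N × ORR × P(involved) × P(discordant):

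- low: 27 × 0.25 × 0.10 × 0.25 = 0.17 patients
- high: 27 × 0.33 × 0.30 × 0.50 = 1.34 patients

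Both figures treat all 27 patients as non-CTCL. MF/SS is eligible, so under these rates the true figure would be lower.

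**The case against.** The strongest reply is that no sentence says every row of a column must hold. The size row is residual, the intent is clear, and an investigator would probably record PR. That is a fair prediction of behaviour, but it does not settle the text. The table writes *Any* where it sets no PET condition, and it does not write *Any* for PR. Following the size row means overriding the PET cell in the same column.

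A second reply is that RECIL 2017 governs and may deal with these cases. That cannot be checked from the documents. Table 14 is what the protocol gives its assessors, and nothing in sections 6.3, 10.3 or 10.4 fills the gap for non-CTCL patients.

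Several stronger readings are tempting and do not hold:

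- *That these patients leave the response rate altogether.* Section 10.4.3 keeps them in the denominator of the all-eligible-patient analysis.
- *That a CT-only visit excludes the patient.* Table 14 is silent on a missing PET, and another visit with PET can qualify.
- *That half the CT evaluations will lack PET.* Section 12.5.2 lists "up to six (6) additional CT scans of the neck, chest, abdomen, and pelvis, and three (3) additional" PET/CT scans. It counts additional research scans only and is not a schedule, so PETs done as clinical care are not in it.
- *That a PR is lost if its confirmatory scan is CT only.* Section 6.3.5 says "best response assignment will depend on the achievement of both measurement and confirmation criteria", but nothing says a RECIL confirmatory scan must satisfy every row of Table 14 again. The explicit repeat-assessment rule in section 6.3.3 is for CTCL.

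**Conclusion.** The point holds for non-CTCL patients. Table 14 states a PET condition for PR that contradicts its own size row and leaves a responder with a negative PET and involved marrow without a category. The missing category for visits without PET is a secondary gap, relevant to a patient only when no other visit with PET qualifies.

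The size is firm per patient (3.7 points at N = 27, 11.1 at N = 9) and unknown in total. Under the assumed rates it is about one patient or fewer, which is small beside an interval some 34 points wide at N = 27. ORR is secondary and descriptive, and the primary endpoints are unaffected. The correction is still worth making before response is analysed, because the rule is wrong as written and costs almost nothing to repair.

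**What to change.** In Table 14:

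1. Change the PR FDG-PET cell to *Any or not done*.
2. Define PR as at least a 30% decrease in the sum of longest diameters, with no new lesion, that does not meet every CR condition.
3. Add the Appendix C fallback: if the repeat marrow is positive, or PET is not done at that evaluation, the response is PR.
4. Leave the PET and marrow requirements for CR as they are.
5. State that this is the protocol's working rule under the RECIL 2017 label, since it may differ from the cited publication.

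Every decrease of at least 30% without a new lesion then falls in CR or PR. The cost is one cell and a few sentences, with no added scans or biopsies. The downside is that a visit without PET can be credited with PR but not CR, so the split between CR and PR still depends on whether PET was done. ORR no longer does.
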